1. General Information / Title Page

Title: Intratympanic Steroid Injection for Treatment of Idiopathic Facial Nerve Paralysis

Working Title: Facial Nerve Study

Project #: 2007139

Version #: 1

Date: 11/21/16

Sponsor: *None*

Faculty Primary Investigator: *[name]*
University of Missouri
Department of Otolaryngology – Head & Neck Surgery
[name]
[name]

Resident Co-Investigator: *[name]*
University of Missouri - Resident Physician
Department of Otolaryngology – Head & Neck Surgery
[name]
[name]

The study will be conducted in accordance with the design and specific provisions of this IRB approved protocol, in accordance with the ethical principles that have their origin in the Declaration of Helsinki, and that are consistent with Good Clinical Practice (GCP) and the applicable regulatory requirement(s). The Principal Investigator will assure that no deviation from, or changes to, the protocol will take place without prior agreement from the sponsor and documented approval from the IRB, except where necessary to eliminate an immediate hazard(s) to the trial participants. The Principal Investigator will promptly report to the IRB and the sponsor any changes in research activity and all unanticipated problems involving risk to human subjects, or others. This trial will be performed in compliance with the protocol, GCP, and all regulatory requirements.

2. Schedule of Events

Recruitment of trial subjects will begin as soon as authorization is granted by the IRB. Clinic and emergency department patterns indicate that we can expect to identify and enroll 20- 25 participants per year. The goal of the study is to include 90 participants over the course of four years and follow until full facial nerve function is recovered or up to 12 months after the completion of treatment, whichever comes first. The expected length of the entire study will vary depending on when all subjects are identified and treatment is completed.

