After obtaining consent, the study participant will undergo a complete history, head, neck, and cranial nerve exam. Facial function will be evaluated with House-Brackmann (H-B) scoring system. For participants with a high suspicion of Lyme disease based on history, Lyme disease serology will be drawn. Electroneurography (ENoG) and electromyography (EMG) testing will be performed on patients with complete facial nerve paralysis. Every participant will be treated with oral steroids (prednisone 60 mg for 5 days followed by a 5 day taper), unless they are unable to for medical reasons.

The study participants will then be randomized into the control group or the treatment group. If randomized to the treatment group, the patient will undergo one intratympanic steroid injection every 3-4 days over the course of 3 weeks for a total of 3 injections. A third group of patients will include those patients that are unable to take oral steroids for medical reasons (such as diabetes); these patients will only receive the intratympanic injection. An audiogram and tympanography testing will be performed on patients that are randomized to receive an intratympanic injection (Group 2) or are placed in Group 3 for medical reasons.

3. Abbreviations

All abbreviations will be defined in parenthesis following their first occurrence in the text.

4. Background Information

Facial nerve paralysis is due to inflammation surrounding the facial nerve. Current clinical practice guidelines for treatment of facial nerve paralysis recommend a 10 day course of oral steroids +/- oral acyclovir. Treatment should begin within 72 hours of symptom onset. In patients with complete facial paralysis, electrodiagnostic testing should be offered to the patient (1-2). In patients with 90% degeneration on electroneuronography (ENoG) testing, facial nerve decompression may be considered but is not a current recommendation.

In 1973, Bryant reported on ten cases where intratympanic steroid injection was used for the treatment of Bell's palsy (3). All but one of these patients had complete recovery of their facial nerve function. The remaining patient had 75% recovery. None of these patients suffered complications from the injections. The next study published on intratympanic steroid injection

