for Bell's palsy was not published until 2014 (4). It was a randomized control trial that divided patients into standard treatment (oral steroids and acyclovir) versus standard treatment with intratympanic steroid injection. There was not a statistically significant difference between the complete recovery rate of the control group and of the intratympanic steroid group; however, the time to recovery was significantly shorter in the intratympanic steroid injection group as compared to the control group. Limitations of this study include small sample size and high attrition rate.

There have not been any other studies published in the literature looking at improving facial nerve recovery in idiopathic facial nerve paralysis with the use of intratympanic steroid injections.

5. Trial Objectives and Purpose

The question proposed by this study are:

Does intratympanic steroid injection improve the complete recovery rate of patients with idiopathic facial nerve paralysis?

Does intratympanic steroid injection hasten the time to recovery in patients with idiopathic facial nerve paralysis?

Are there significantly more adverse effects with the use of intratympanic steroid injection as compared to oral steroids in patients with idiopathic facial nerve paralysis?

The trial seeks to provide evidence that intratympanic steroid injection are acceptable and successful adjuncts to treatment of idiopathic facial nerve paralysis.

To answer this question, a prospective, single-blinded, randomized trial will be performed. The subjects will be randomized into the treatment group and the control group. The control group will receive oral steroids which is the current standard of care. Patients in the treatment group will receive oral steroids AND intratympanic steroid injections. The patient's will not be blinded because the patient will be undergoing an in-office procedure. It has been found to be unethical to perform sham procedures in patients. A third group of patients will consist of those patients that are unable to take oral steroids for medical reasons. These patients will only receive the intratympanic injection and they are placed in this group for medical reasons only (no randomization into this group). The patients will be examined and scored using House-Brackmann scoring system by a blinded investigator trained in otolaryngology.

6. Trial Design

Design:

Prospective, randomized, single-blinded clinical trial

Protocol: *Facial Nerve Study*

PI: [name]

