Efficacy of the treatment will be assessed by measuring facial nerve function using the H-B scale I-VI. Two blinded trained otolaryngologist or mid-level provider trained in otolaryngology will determine the efficacy by evaluating each individual study subject via video recording.

10. Assessment of Safety

Risks of intratympanic steroid injections include pain, bleeding, vertigo, otitis media, and tympanic membrane perforation.

The presence or absence of tympanic membrane perforation will be documented at 14 days and 1 month post-treatment. If a perforation is present, the extent of the perforation, type of treatment, and when resolved will be recorded.

All adverse events will be reported to the IRB and the Otolaryngology Department Quality Assurance. Admission of a trial participant to an emergency room or hospital will be recorded.

11. Statistics

A sample calculation was performed for the number of subjects to be enrolled in order to prove superiority of oral steroids + intratympanic steroids over oral steroids alone. The assumption was made that a 20% increase in primary outcome of complete recovery would be significant. A sample size of 25 subjects should detect a difference at a power greater than 80% and an alpha of 0.05. To account for potential testing or data collection errors, we will collect data on 30 subjects treated with oral steroids and intratympanic steroid injections, as well as 30 controls treated with oral steroids only, for a total of 60 subjects. Data will be collected on up to 30 additional subjects that are placed into Group 3 for medical reasons; therefore total number of subjects to be recruited is 90.

12. Direct Access to Source Data/Documents

The investigators will permit study-related monitoring, audits, IRB/IEC review, and regulatory inspection(s) by providing direct access to source data/documents.

13. Quality Control and Quality Assurance

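### Section 11's claim of more than 80% power with 25 subjects cannot be reproduced: for assumed control recovery of 40-75%, a 20-point gain has about 29-51% two-sided power at 25 per arm and 34-59% at 30 per arm

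*Combined protocol and SAP*

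**What the plan says.** Section 11 (Statistics) says the calculation was done "in order to prove superiority of oral steroids + intratympanic steroids over oral steroids alone". Its effect size is: "The assumption was made that a 20% increase in primary outcome of complete recovery would be significant". Its result is: "A sample size of 25 subjects should detect a difference at a power greater than 80% and an alpha of 0.05". The number is then raised: "To account for potential testing or data collection errors, we will collect data on 30 subjects" in the injection arm and the same number of controls, so 60 are randomized. Up to 30 more patients enter Group 3 without randomization and add nothing to this comparison.

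The section does not give:
- the control recovery rate or a source for it;
- the test or its sidedness;
- whether the 20% is absolute or relative;
- whether 25 is per arm or in total (the step to 30 in each arm suggests per arm).

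Section 4 (Background Information) gives one recovery figure, from an uncontrolled series of ten injected patients: "All but one of these patients had complete recovery of their facial nerve function". Of the earlier randomized trial it says: "There was not a statistically significant difference between the complete recovery rate of the control group and of the intratympanic steroid group", and adds: "Limitations of this study include small sample size and high attrition rate". Section 2 (Schedule of Events) says of recruitment: "we can expect to identify and enroll 20- 25 participants per year", with a goal of 90 over four years.

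**The concern.** With a binary outcome and 25 patients per arm, the standard error of a difference in proportions is about 10 to 14 points when recovery rates are in the middle to upper range. A 20-point difference is then only about 1.4 to 2.1 standard errors, whereas 80% power at two-sided 0.05 needs about 2.8 (1.96 + 0.84). The stated power looked too high by a wide margin.

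This calculation is the only justification for the size of the randomized comparison. If the true power is near or below one half, a real 20-point benefit could easily be missed, and a reader relying on the stated power would take the non-significant result as good evidence of no benefit. By the protocol's own account the earlier randomized trial was non-significant on this outcome and was small. This one could repeat that inconclusive result.

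**Working it through.** **Inputs from section 11.** Alpha 0.05; claimed power above 80%; increase of 20%; 25 subjects, raised to 30 per arm; 1:1 allocation.

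**Assumptions.** The control rate p1 is not in the documents, so it is varied from 40% to 75%. The 20% is read as 20 percentage points and 25 as per arm, the readings that give the highest power.

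**Formula (pooled two-proportion, two-sided).** With p2 = p1 + 0.20 and p̄ = (p1 + p2)/2:

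se0 = √[2p̄(1−p̄)/n], se1 = √[(p1(1−p1) + p2(1−p2))/n], power = Φ[(0.20 − 1.96·se0)/se1].

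**Attempt to reproduce the plan's figure, 70% vs 90%, n = 25 per arm.** This example pairs the 90% in the ten-case series with a control rate 20 points lower.
- se0 = √(2 × 0.80 × 0.20/25) = 0.1131, and 1.96 × 0.1131 = 0.2217.
- se1 = √((0.21 + 0.09)/25) = 0.1095.
- Power = Φ[(0.20 − 0.2217)/0.1095] = Φ(−0.198) = 0.42, against a claim of more than 0.80.

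**Across the assumed range:**

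| Control → treated | Power, 25/arm | Power, 30/arm | n per arm for 80% |
|---|---|---|---|
| 40 → 60% | 0.29 | 0.34 | 97 |
| 50 → 70% | 0.30 | 0.35 | 93 |
| 60 → 80% | 0.33 | 0.39 | 82 |
| 70 → 90% | 0.42 | 0.49 | 62 |
| 75 → 95% | 0.51 | 0.59 | 49 |

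The last column uses n = [1.96√(2p̄(1−p̄)) + 0.842√(p1(1−p1) + p2(1−p2))]²/0.20². For 70 → 90% this is (1.1087 + 0.4610)²/0.04 = 61.6, rounded up to 62. The total randomized would be 98 to 194.

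For a 20-point difference the formula is symmetric about a control rate of 40%, so control rates of 5-40% give the same range.

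**Other methods, two-sided, control 40-75% in 1-point steps:**

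| Method | 25/arm | 30/arm |
|---|---|---|
| Unpooled normal | 0.30-0.54 | 0.35-0.62 |
| Arcsine | 0.30-0.56 | 0.34-0.64 |
| Pearson chi-square, exact enumeration | 0.33-0.56 | 0.35-0.63 |
| Likelihood-ratio chi-square, exact enumeration | 0.33-0.57 | 0.35-0.66 |
| Fisher exact | 0.23-0.37 | 0.26-0.44 |

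One-sided, the pooled formula gives 0.41-0.64 at 25 per arm and 0.46-0.71 at 30. The highest one-sided value of any of the six methods is 0.69 at 25 and 0.76 at 30 (likelihood-ratio, 75 → 95%).

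**Less favourable readings (pooled, two-sided).** If 25 is a total (12.5 per arm), power is 0.16-0.28. If the increase is relative, power at 25 per arm is 0.08 (40 → 48%) to 0.28 (75 → 90%).

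**What 30 per arm can do.** The increase detectable with 80% power is about 35 points from a control rate of 40%, falling to 24 points from 75%. For a 20-point difference the 95% CI half-width, 1.96·se1, is about 25 points (40 → 60%) to 17 points (75 → 95%).

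**Margin and accrual.** The step from 25 to 30 allows for 5/30 = 16.7% loss. With 20 evaluable per arm (an assumed 33% loss), power is 0.24-0.42. Expected accrual is 20 × 4 = 80 to 25 × 4 = 100 patients across all three groups. If all 90 places were randomized (45 per arm), power would be about 0.47-0.77.

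**The case against.** The control rate is the crux, and the range used here is assumed. Its upper end, 75%, stops just short of where some methods cross 80%. At 25 per arm the two-sided likelihood-ratio test reaches 0.80 for 79 → 99%. At 30 per arm one-sided tests reach 0.81 for 76.5 → 96.5%. Nine recoveries in ten patients has an exact 95% CI of about 55% to 99.7%, so the background series cannot exclude treated recovery that high. This stands as a limit on the finding: the claim is not impossible under every input. But the plan does not state near-complete recovery as its assumption, and at 79 → 99% with 25 per arm the other two-sided tests still fall short (pooled 0.62, Pearson 0.71, Fisher 0.39).

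Two other calculations come closer. A one-sided, one-sample exact test of 25 treated patients against a fixed 75%, with 95% as the alternative, has 87% power and may be where the figure came from. It ignores sampling error in the control arm and does not fit a randomized two-arm comparison. A log-rank approximation for time to recovery, assuming proportional hazards and full follow-up, gives 71% two-sided and 81% one-sided at 25 per arm for 75 → 95%. For control rates of 40-70% its two-sided power is only 31-54%, and section 11 names complete recovery, not time to it, as primary.

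It is also fair to say that section 2 leaves the length of the study open, so longer recruitment is possible, and that dropping the superiority wording is a reporting preference rather than a correction of arithmetic.

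**Conclusion.** The concern holds. The stated power cannot be reproduced from anything in the documents. For a 20-point increase and control recovery of 40-75%, two-sided pooled power is 29-51% at 25 per arm and 34-59% at 30, and none of the six two-arm methods reaches 80% on either sidedness. At 30 per arm, every two-sided method gives 26-47% for control rates of 40-65%, so a true 20-point benefit would more likely than not be missed. At a 70% control rate the chance is roughly even (37-54%).

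The conclusion rests on the assumed control range, on 20% being absolute and on 25 being per arm. The last two favour the plan. It would change only if treated recovery were within about 4 points of 100%, and then only for some tests. The power statement must be corrected.

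**What to change.** In section 11:

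1. State the assumed control recovery rate with its source, the test and its sidedness, whether the 20% is absolute, and whether 25 is per arm.
2. Replace the power sentence with a recalculated one. If no control rate can be sourced, give a range and label it as assumed, for example: *with 30 per arm (25 evaluable), power for a 20-point increase is about 34-59% (29-51%) for control recovery of 40-75%, two-sided alpha 0.05; with 30 per arm, 80% power requires an increase of about 24 to 35 points.*
3. State whether the margin from 25 to 30 also covers loss to follow-up.
4. Preferably, drop the language of proving superiority, report the Group 2 minus Group 1 difference in complete recovery with its 95% CI as the primary result, and state that non-significance will not be read as no benefit.

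This changes wording in section 11 only. It needs no extra patients, visits or tests; its cost is a less favourable stated power. Enlarging the trial is the alternative, but 98 to 194 randomized patients would take nearly all, or more than all, of the 80-100 expected over four years and leave almost no room for Group 3. If the sponsor prefers that route, the recruitment period would have to be extended.
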